15. EFFICACY OUTCOMES

At each visit, three serial sitting BP measurements will be obtained and the average (arithmetic mean) of the 3 serial measurements will be used for the efficacy analysis.

15.1. PRIMARY EFFICACY

15.1.1. Primary Efficacy Variable(s) & Derivation(s)

Change from Week 6/Final Visit of the DB Phase to Week 8/Final Visit of the Withdrawal Phase in trough clinic seated diastolic blood pressure (seDBP) between AZM and placebo which is collected in the eCRF.

Document: 2014-000674-18 Statistical Analysis Plan Version 7.0 Version Number: 7.0

Author: Version Date: 13JAN2020

Template No.: CS_TP_BS016 Revision 5 Reference: CS_WI_BS005

Effective Date: 01Apr2018

15.1.2. MISSING DATA METHODS FOR PRIMARY EFFICACY VARIABLE(S)

The primary analysis will use multiple imputations for missing data, supported by sensitivity analysis using observed data. Multiple imputation is a stochastic parameter estimation method for partially observed data. Missing data will be assumed to follow an arbitrary missing data pattern, and a multivariate response model will be fitted separately for each treatment group using the Markov Chain Monte Carlo (MCMC) method. This method of imputation draws each missing value from its conditional distribution, given the observed data (baseline and post baseline values of the parameter) expected to be predictive of the missing pattern. Details on MCMC method is found in Appendix 5.

15.1.3. Primary Analysis of Primary Efficacy Variable(s)

The primary objective of this study is to evaluate the antihypertensive effect of AZM compared with placebo after a randomized, double-blind, withdrawal (Withdrawal Phase).

The primary efficacy analysis will be performed for the FAS. The primary analysis will exclude subjects that were treated with losartan during the DB Phase.

The primary efficacy variable analysis will be an ANCOVA model with treatment (AZM low, med, high and placebo), age (Tanner stage <3, ≥3), race (Black or African American, Non- Black or African American) and weight (<50 kg, ≥50 kg) as fixed effects, and Week 6/Final Visit of the DB Phase seDBP as a covariate. The primary comparison, mean (i.e. pooled) AZM effect versus placebo, will be made using an ANCOVA contrast statement. Comparisons between each AZM dose to placebo will also be done from the framework of the above ANCOVA using contrast statements.

To control for multiplicity of the type 1 error, the sequential testing procedure mentioned in Section 7.4 will be employed in the analysis of the primary endpoint.

Summary of observed seDBP at Week 6 and Week 8 will be presented. Change in seDBP from Week 6 to Week 8 and the results from the analysis (Least square (LS) means, Standard Error, LS Mean Difference (SE), P-value and 95% Confidence Interval for Difference in LS means) will also be presented.

Profile plots (line with symbol at each visit with +/- 1 SE error bars) will be displayed for observed seDBP and boxplot will be displayed for the change in seDBP from Week 6 to Week 8.

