4.2 Rationale for the Proposed Study

To better understand the safety and efficacy of AZM as a treatment option for pediatric patients with primary or secondary hypertension, and in accordance with legislative and regulatory requirements both in the US and European Union (EU), Arbor has designed a pediatric development program for AZM. The main elements of the pediatric program include: (1) a pharmacokinetic study in children and adolescents and gender-matched healthy adults, (2) a phase 3 efficacy and safety study in children and adolescents (6 to <18 years), and (3) a phase 3 efficacy and safety study in young children (≥ 12 months and <25 kg). The scope and objectives of these studies have been presented to the Food and Drug Administration (FDA) as part of the Pediatric Research Equity Act (PREA) commitments and the Best Pharmaceuticals for Children Act (BPCA), in addition to the European Medicines Agency (EMA) as part of the Pediatric Investigation Plan (PIP) commitments.

The pharmacokinetic study, TAK-491_109 [\[21\]](#), was the first of the 3 pediatric studies to be initiated and results are available for the cohorts of subjects 6 to <17 years of age; as described in [Section 6.2](#), data from these subjects provide support to proceed with the present efficacy and safety study (AR14.0001) in the 6 to 17 year age group. The present study is designed to evaluate 4 doses of AZM in the low, intermediate, and high dose treatment arms during 6 weeks of double-blind, randomized treatment (Double-Blind [DB] Phase), and to compare AZM to placebo and an active comparator (losartan) after a 2-week, double-blind, randomized withdrawal (Withdrawal Phase); the long-term safety and efficacy of AZM will also be evaluated during a 44-week, OL extension (OL Phase).

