5.1.2 Secondary Objectives

To evaluate the antihypertensive effect of AZM compared with losartan during double-blind treatment (Double-Blind Phase).

To evaluate the safety and tolerability of AZM relative to placebo and losartan during double-blind treatment, and of AZM during a long-term, OL extension (OL Phase).

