6.1.6 Randomization Procedures

The investigator or investigator's designee will access the IVRS/IWRS at Screening to obtain the subject's study number. The investigator or the investigator's designee will utilize the IVRS/IWRS to enter the subject into the Placebo Run-in Phase. The IVRS/IWRS will also be used to randomize the subject into the DB Phase and later the Withdrawal Phase. The DB Phase randomization will be stratified by age (Tanner stage <3, ≥ 3), weight (≥ 25 to < 50 kg, ≥ 50 kg), and race (non-Black, Black). Enrollment caps will also be applied to randomization to ensure a percentage of subjects with secondary hypertension of approximately 20% and to ensure that no more than $\approx 25\%$ of subjects are post-renal transplant patients and no more than $\approx 80\%$ of subjects

weigh greater than or equal to 50 kg at Baseline Randomization for the Withdrawal Phase will be stratified by the treatment received in the DB Phase (ie, AZM-L, AZM-M, or AZM-H or losartan).

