13.3 Determination of Sample Size

Prior to study start:

Assuming an SD of 10.5 mm Hg and an overall 10% dropout rate (ie, the DB and Withdrawal Phases), 195 subjects randomized to AZM into the DB Phase (65/arm) will provide 80% power to detect a difference of 4.5 mmHg between AZM (pooled) and placebo by a 2-sample t-test of the mean seDBP change from Week 6/Final Visit of the DB Phase to Week 8/Final Visit of the Withdrawal Phase at the 0.05 significance level (2-sided).

Revised Sample Size Justification:

Upon review of pooled blinded data of the primary endpoint, the SD was 7.82 which was much less than what was previously specified. Taking into consideration variability in the SD, an SD estimate of 8.3 is used in the revised sample size (all other assumptions being the same) below.

Assuming an SD of 8.3 mm Hg and an overall 10% dropout rate (ie, the DB and Withdrawal Phases), approximately 208 subjects randomized to AZM or losartan during the DB Phase (52/arm) will provide >80% power to detect a difference of 4.5 mmHg between AZM (pooled) and placebo by a 2-sample t-test of the mean seDBP change from Week 6/Final Visit of the DB Phase to Week 8/Final Visit of the Withdrawal Phase at the 0.05 significance level (2-sided).

CONFIDENTIAL

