15.2.3. Analysis of Secondary Efficacy Variables

15.2.3.1.

Change from Week 6/Final Visit of the DB Phase to Week 8/Final Visit of the Withdrawal Phase in trough clinic seSBP and MAP will be analyzed using an ANCOVA model with treatment (AZM low, med, high and placebo), age (Tanner stage <3, ≥3), race (Black or African American, Non- Black or African American) and weight (<50 kg, ≥50 kg) as fixed effects, and baseline value (seDBP or MAP) as a covariate. The comparison, mean (i.e., pooled) AZM effect versus placebo, will be made using an ANCOVA contrast statement. Comparisons between each AZM dose to placebo will also be done from the framework of the above ANCOVA using contrast statements.

This analysis will exclude subjects that were treated with losartan during the DB Phase. There will be no sequential testing procedure for this analysis.

Profile plots (line with symbol at each visit with +/- 1 SE error bars) will be displayed for observed seSBP and MAP and boxplot will be displayed for the change in seSBP and MAP from Week 6 to Week 8.

15.2.3.2.

Change from baseline in trough clinic seDBP, seSBP, and MAP at Week 6/Final Visit, will be analyzed with a mixed models for repeated measure (MMRM) with treatment (AZM low, med, high dose and losartan), time point (Week 2, Week 4, Week 6), treatment by time interaction, age (Tanner stage <3, ≥3), race (Black or African American, Non- Black or African American) and weight (<50 kg, ≥50 kg) as fixed effects, and corresponding baseline value (seDBP, seSBP, MAP) as a covariate. An unstructured covariance matrix will be used to model the within-subject variation-covariance errors. The comparison, mean (i.e., pooled) AZM effect versus losartan, will be made using contrast statement. Comparisons between each AZM dose to losartan will be done from the framework of the above MMRM. Observed data will be used to perform MMRM. Sensitivity analyses will be performed including ANCOVA at each time point using last observation carried forward (LOCF).

In case of non-convergence, the following tests in sequence will be used: heterogeneous Toeplitz covariance structure, heterogeneous autoregressive covariance structure, heterogeneous compound symmetry covariance structure.

Profile plots (line with symbol at each visit with +/- 1 SE error bars) will be displayed for the change in seDBP, seSBP and seMAP from baseline to Week 6.

15.2.3.3.

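### No planned analysis compares losartan with its own randomised placebo in the Withdrawal Phase, so the plan reports no placebo-controlled estimate for its active comparator

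*SAP*

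**What the plan says.** **Design.** Protocol 6.1 and Figure 8.a re-randomise every DB arm 1:1 to active drug or placebo at Week 6, losartan included. Protocol 6.1.6 makes this randomisation "stratified by the treatment received in the DB Phase (ie, AZM-L, AZM-M, or AZM-H or losartan" (8.3 agrees). Losartan versus losartan-to-placebo is therefore a randomised comparison within one stratum.

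**Change analyses.** For the primary endpoint, SAP 15.1.3 says: "The primary analysis will exclude subjects that were treated with losartan during the DB Phase". The observed-data sensitivity analysis (15.1.4) reuses that model. For seSBP and MAP, SAP 15.2.3.1 says: "This analysis will exclude subjects that were treated with losartan during the DB Phase".

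**Other Withdrawal Phase models.** The Withdrawal treatment factor in SAP 7.1, the Week 8 target-BP model in 15.2.3.3 and the code in Appendix 5 all have three AZM levels and placebo, with no losartan level. Subgroup tests (7.5) compare pooled AZM with placebo. The CKD target-BP model in 15.3.3.3, which also covers Week 8, lists losartan but no placebo. No model contains both.

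**Displays.** SAP section 9 and Appendix 1 list Placebo, Losartan and the three AZM doses for the Withdrawal Phase. Placebo is one group, not divided by the drug taken before.

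**Role of losartan.** Protocol 5.1.2 gives as a secondary objective: "To evaluate the antihypertensive effect of AZM compared with losartan during double-blind treatment (Double-Blind Phase". Protocol 6.2.3 confines placebo to the run-in and the Withdrawal Phase. Protocol 6.2.4 supports losartan's efficacy from outside sources. Protocol 4.2 describes the study as designed "to compare AZM to placebo and an active comparator (losartan) after a 2-week, double-blind, randomized withdrawal (Withdrawal Phase".

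**The concern.** The DB Phase comparison of AZM with losartan has no concurrent placebo. If AZM looks better, a reader cannot tell from that comparison whether AZM is the stronger drug or losartan did little in this sample. If the two look alike, the primary result on AZM gives only indirect support for losartan. The trial's only randomised information on losartan against placebo lies in the losartan stratum of the Withdrawal Phase, and no planned analysis draws on it.

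About 26 children (52 / 2) are switched from losartan to placebo. Their Week 6 and Week 8 pressures are collected, but enter no contrast with the children who stayed on losartan. At stake is how well a secondary comparison can be interpreted. The primary objective, its power and its type I error are not affected.

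**Working it through.** **Inputs**, all from Protocol 13.3 (repeated in SAP 3.5):
- Two-sided 5% test: "Week 8/Final Visit of the Withdrawal Phase at the 0.05 significance level (2-sided".
- SD: "an SD estimate of 8.3 is used in the revised sample size". The blinded pooled SD was 7.82; the assumption before the study was 10.5.
- 52 per arm, so 156 AZM and 52 losartan; 10% dropout over both phases.
- Target effect 4.5 mm Hg, stated for AZM only. No figure is given for losartan, so 4.5 is assumed for it below.

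**Formulae**, with n per group:
- SE = SD × √(2/n)
- 95% half-width = t(0.975, 2n − 2) × SE
- Power from the noncentral t distribution with noncentrality 4.5/SE

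**Step 1: the plan's own figures.**
- Before study start (SD 10.5): 87 per group are needed; 174 / 0.9 = 193.3, rounded up to 194, against 195 stated.
- Revised: the plan says 52 per arm "will provide >80% power to detect a difference of 4.5 mmHg between AZM (pooled) and placebo by a 2-sample t-test". 156 × 0.9 / 2 = 70.2 per group; SE = 8.3 × √(2/70.2) = 1.40; noncentrality 3.21; power 89%. The claim holds and does not need the losartan arm.

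**Step 2: is the exclusion sound?** Losartan-to-placebo children were not randomised against the AZM children within a Withdrawal stratum. Counting them as extra placebo (70.2 vs 93.6) would raise power only from 89.1% to 92.7%. Leaving them out costs little and keeps the comparison randomised.

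**Step 3: the missing contrast.** 52 × 0.9 / 2 = 23.4 per group. At SD 8.3, SE = 8.3 × √(2/23.4) = 2.43 and noncentrality = 4.5 / 2.43 = 1.85.

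| n per group | SD (mm Hg) | 95% half-width (mm Hg) | Power for 4.5 mm Hg |
|---|---|---|---|
| 23.4 | 7.82 | 4.6 | 49% |
| 23.4 | 8.3 | 4.9 | 44% |
| 23.4 | 10.5 | 6.2 | 30% |
| 26 (no dropout) | 8.3 | 4.6 | 48% |

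At 23.4 per group and SD 8.3, the difference detectable with 80% power is about 6.9 mm Hg. Having 80% power for 4.5 mm Hg would take 55 per group: 110 / 0.9 = 122.2, or 123 losartan children in the DB Phase, against 52 planned.

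**Step 4: difference between the AZM and losartan effects.** SE = √(8.3² × 2/70.2 + 8.3² × 2/23.4) = 2.80; half-width = 1.96 × 2.80 = 5.5 mm Hg.

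These are two-sample calculations. An ANCOVA adjusting for the Week 6 value could narrow the intervals, by an amount the documents do not allow one to estimate.

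**The case against.** The case for leaving the plan alone has several parts.

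- **Losartan's efficacy is not an objective or endpoint.** This is true. The operative objectives and endpoints place the losartan comparison in the DB Phase, where the SAP analyses it by MMRM with no stated non-inferiority or equivalence margin. Protocol 6.2.4 justifies losartan at the study doses from outside evidence. That is a fair reason for choosing the comparator, but it is not evidence from this sample.
- **The primary analysis already shows whether the trial can detect a BP effect.** It does so for AZM. It does not say how losartan performed.
- **The contrast is too imprecise to settle anything.** This largely stands. The half-width of 4.9 mm Hg exceeds the 4.5 mm Hg effect, so an estimate exactly on target would still have an interval crossing zero. It limits what may be claimed, but is no reason to report no estimate.
- **The data are not wholly unreported.** This also stands. Losartan is a displayed Withdrawal group, and SAP sections 16 and 16.4 summarise seated BP change by treatment from the last DB value, so change in continuing losartan children will be shown. The table templates mentioned in SAP section 8 are not among the documents, so the single Placebo column is inferred from the group labels.
- **Protocol 13.1.3 permits additional analyses where appropriate.** It does, but one chosen after unblinding would be post hoc.

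Two stronger readings are tempting. A reader might infer that the trial cannot show whether losartan worked, or that it throws the information away. The documents do not support this: the re-randomisation is stratified and the pressures are collected, so the gap is in the analysis plan and not in the design. A reader might also infer that Protocol 4.2 promises a placebo-adjusted AZM-versus-losartan comparison. It does not: it is one sentence of rationale naming both comparators, with no such adjustment described.

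**Conclusion.** The point holds as a gap in planned reporting. The losartan stratum is randomised to losartan or placebo, no model contrasts the two, and the group labels combine placebo children from both sources. As written, the plan gives no placebo-controlled estimate for the active comparator. The exclusion quoted from SAP 15.1.3 is correct.

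The missing contrast would rest on about 23 children per group, with a 95% half-width of about 4.9 mm Hg and about 44% power for 4.5 mm Hg. This assumes SD 8.3, 10% dropout, equal splitting and the AZM target effect for losartan; across the documents' three SDs power runs from 30% to 49%. A null result would not show that losartan failed. The contrast should not be presented as *the* assay-sensitivity evidence for the DB comparison: it is imprecise, and it measures change over two weeks of withdrawal, whereas the DB comparison concerns six weeks of treatment. Any difference between the AZM and losartan effects (half-width about 5.5 mm Hg) is descriptive only.

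This is a cheap improvement. The primary analysis needs no change.

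**What to change.** Keep the primary analysis and its exclusion. Before the unblinding described in SAP 4.2:

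1. Add to SAP 15.2.3.1 a supportive analysis, outside the testing sequence, of the Week 6 to Week 8 change in seDBP, seSBP and MAP for losartan versus losartan-to-placebo. Use the same ANCOVA within the losartan stratum and report the estimate with its 95% CI.
2. Show *Placebo (from AZM)* and *Placebo (from losartan)* as separate columns in the Week 6/Week 8 BP summaries.
3. State the limits beside the result: about 23 per group, half-width about 4.9 mm Hg, about 44% power for an assumed 4.5 mm Hg, and no inference of failure from a null result. If the difference between the AZM and losartan effects is reported, label it descriptive.
4. In the same edit, say in 15.2.3.3 whether losartan-to-placebo children count as placebo in the Week 8 target-BP model, and correct the treatment levels of the CKD Week 8 model in 15.3.3.3.

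The cost is SAP wording, one model applied to three variables and one split column, with no new data or patients. The downside is wide intervals from about 47 children (52 × 0.9), which readers may over-interpret unless the supportive label is plain.

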6.1.4 Double-Blind, Randomized Treatment Phases

6.1.4.1 Double-Blind Phase

Qualified subjects who meet the BP entry requirements (ie, seDBP ≥ 95 th percentile for age, gender, and height or ≥ 90 th percentile for age, gender, height if chronic renal disease, diabetes, heart failure or hypertensive target organ damage is present), including at Day -1/Visit 3 (or Day 1 for subjects not participating in ABPM) will be eligible for randomization. Currently treated subjects who have washed out of their antihypertensive medications but have a BP that remains

below the entry criteria at Day -1 (or Day 1 for subjects not participating in ABPM) may extend the Washout/Run-in Period as described in [Section 6.1.2](#) as long as SBP also remains below the same threshold.

After a qualifying clinic seDBP has been confirmed and anthropomorphic measurements have been recorded, subjects who agree to participate in the ABPM procedure will be fitted with an ABPM device that will be worn for at least 24 hours. After the ABPM device is removed on Day 1/Visit 4, pretreatment vital signs and a full panel of clinical laboratory tests will be completed. Subjects who do not participate in the ABPM procedure will not visit the clinic on Day -1; for these subjects, the qualifying seDBP will be confirmed on Day 1 before randomization.

After the baseline procedures are conducted on Day1/Visit 4, all qualifying subjects will receive their first dose of randomized, double-blind study medication at the investigative site, and study medication will be dispensed. Study medication will be administered orally with water, at an agreed upon (by the site and subject) consistent time of day, with or without food, and will be administered in the clinic on days when a visit is scheduled.

Additional clinic visits will be scheduled at Weeks 2, 4, and 6 of the DB Phase. A renal subpanel (sodium, potassium, chloride, blood urea nitrogen [BUN], creatinine, cystatin C, estimated glomerular filtration rate [eGFR]) will be collected at Week 4/Visit 6, which corresponds to 2 weeks after study drug is force-titrated. The renal subpanel may be completed at an earlier unscheduled visit (ie, 5 to 7 days after Week 2/Visit 5) at the investigator's discretion.

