7.1 Inclusion Criteria

Subject eligibility is determined according to the following criteria:

1. In the opinion of the investigator, the subject or parent/legal guardian is capable of understanding and complying with the protocol requirements.
2. The subject is capable of understanding (as far as their cognitive ability allows and as judged by the investigator and parent/legal guardian) an informed assent form or consent form (if of an appropriate age) and verbal explanations by the investigator. The subject is willing to give their written assent (if required by IRB/IEC) or consent (if of an appropriate age) to participate.
3. The subject's parent/legal guardian, if signing consent on behalf of their child, must (1) have understood the information contained in the informed consent document and had an opportunity to ask questions of the investigator and understands the answers, and (2) sign and date a written informed consent form on behalf of their child prior to the initiation of any study procedures.
4. The subject has hypertension (primary or secondary) defined as clinic seDBP \geq 95th percentile (by age, gender, and height) or \geq 90th percentile (by age, gender, height) if chronic renal disease, diabetes, heart failure or hypertensive target organ damage is present.
 - a) If currently treated: The subject has a documented historical diagnosis of hypertension AND a post-washout clinic seDBP meeting the above criteria on Day -1 (or Day 1 for subjects not participating in ABPM).
 - b) If currently untreated: The subject has elevated seDBP meeting the above criteria on 3 separate occasions before Randomization, including on Day -1 (or Day 1 for subjects not participating in ABPM).
5. The subject is male or female and aged 6 to $<$ 18 years at Baseline and weighs at least 25 kg.
6. Subjects $<$ 50 kg must have the ability to swallow a capsule or tablet with a maximum size of 15.64 mm in length and 7.42 mm in thickness, while subjects \geq 50 kg must have the ability to swallow a tablet or capsule with a maximum size of 16.19 mm in length and 8.30 mm in thickness.
7. The subject agrees to continue their previously implemented nonpharmacological life style modifications if begun prior to Screening. Note: For subjects participating in a weight loss program, the weight maintenance phase must have begun at least 30 days prior to Screening/Visit 1.

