13.1.3 Efficacy Analysis

Unless otherwise specified all statistical tests will be 2-sided, and p-values will be rounded to 3 significant digits prior to assessing for statistical significance at the 0.05 level

The primary analysis for the primary endpoint, change from Week 6/Final Visit of the DB Phase to Week 8/Final Visit of the Withdrawal Phase in clinic seDBP, will be an analysis of covariance (ANCOVA) model with treatment (AZM low, med, high and placebo), age (Tanner stage <3, ≥ 3) and weight (<50 kg, ≥ 50 kg) as fixed effects, and Week 6/Final Visit of the DB Phase seDBP as covariate. For the primary analysis the placebo group will exclude subjects that were treated with losartan during the DB Phase. The primary comparison, mean (ie, pooled) AZM effect versus placebo, will be made using ANCOVA contrast statement. Comparisons between each AZM dose to placebo will also be done from the framework of the above ANCOVA using contrast statements. To control for multiplicity of the type 1 error, the following sequential testing procedure will be employed in the analysis of the primary endpoint using the above described ANCOVA model and contrast statements: Step 1, the mean AZM effect versus placebo will be tested, if statistically significant then testing will continue to the next step; Step 2, AZM high dose effect versus placebo will be tested, if statistically significant then testing will continue to the next step; Step 3, AZM med dose effect versus placebo will be tested, if statistically significant then testing will continue to the next step; Step 4, AZM low dose effect versus placebo will be tested .

The primary analysis will use multiple imputations for missing data, supported by sensitivity analysis using observed data. Multiple imputations is a stochastic parameter estimation method for partially observed data. Missing data will be assumed to follow an arbitrary missing data pattern, and a multivariate response model will be fitted separately for each treatment group using the Markov Chain Monte Carlo method. This method of imputation draws each missing value from its conditional distribution, given the observed data (baseline and post baseline values of the parameter) expected to be predictive of the missing pattern.

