APPENDIX 5. Monte Carlo Markov Chain (MCMC)

MONTE CARLO MARKOV CHAIN (MCMC)

• Step 1: PROC MI will be applied to create monotone data.

```
SUBJID – subject ID number
TRT – Treatment Arm – Placebo (TRT=4), AZM-L (TRT=1), AZM-M (TRT=2) and AZM-H (TRT=3))
TRT1 – AZM-L Arm
TRT2 - AZM-M Arm
TRT3 - AZM-H Arm
WGTGRP – Weight group (<50, >=50)
TANSGRP – Tanner Stage (< 3, >=3)
RACEGRP – Race Group (Black or African American, Non-Black or African American)
SCORE_0 - seDBP at time-point 0 (BASELINE, D1)
SCORE_1 - post-baseline visits 1(W2)
SCORE 2 - visit 2 (W4)
SCORE 3 - visit 3 (W6/final visit of DB phase)
SCORE 5 - visit 5 (w8/final visit of WD phase)
proc mi data=datain out=datain_mono nimpute=100 seed=123;
  var trt1 trt2 trt3 wgtgrp tansgrp racegrp score 0 score 1 score 2 score 3 score 5;
mcmc chain=multiple impute=monotone;
run;
proc sort data=datain mono;
by Imputation trt;
run;
```

• Step 2: PROC MI will be applied to the monotone data to complete the imputation.

```
proc mi data=datain_mono out=datain_reg seed=465 nimpute=1;
by _imputation_ trt;
var trt wgtgrp tansgrp racegrp score_0 score_1 score_2 score_3 score_5;
class trt wgtgrp tansgrp racegrp;
monotone regression;
run;
```

 Step 3: Transform the imputed dataset so that for each subject, we will compute a change from Week 6/Final Visit of the DB Phase to Week 8/Final Visit of Withdrawal Phase in the trough seated diastolic blood pressure (seDBP)

data datain reg1;

Document: 2014-000674-18 Statistical Analysis Plan Version 7.0

Author: Version Number: 7.0

Version Date: 13JAN2020

Reference: CS_WI_BS005

Effective Date: 01Apr2018

```
set datain_reg;
score_c=score_5 - score_3;
run;
         Step 4: PROC MIXED
proc mixed data=datain_reg1;
by _imputation_;
class trt;
model score_c= trt wgtgrp tansgrp racegrp score_3/solution covb;
ods output Ismestimates=est_mi;
Ismeans trt/diff=control('4') cl;
Ismestimate trt 'Pooled AZM vs Placebo' 1 1 1 -3/divisor=3 cl;
Ismestimate trt 'AZM-L vs Placebo' 1 0 0 -1;
Ismestimate trt 'AZM-M vs Placebo' 0 1 0 -1;
Ismestimate trt 'AZM-H vs Placebo' 0 0 1 -1;
Ismestimate trt 'AZM-L' 1 0 0 0;
Ismestimate trt 'AZM-M' 0 1 0 0;
Ismestimate trt 'AZM-H' 0 0 1 0;
Ismestimate trt 'Placebo' 0 0 0 1;
Ismestimate trt 'AZM-Pooled' 1 1 1 0/divisor=3 cl;
run;
         MIANALYZE
```

Step 5: Results from all ANCOVA analysis are then combined together for overall inference using PROC

```
proc sort data=est_mi;
by label;
run;
proc mianalyze data=est mi;

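### The primary ANCOVA uses Week 6 seDBP as its only blood pressure covariate and leaves out Day 1 seDBP, missing a modest gain in precision

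*SAP*

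**What the plan says.** The primary endpoint is the change in trough seDBP from Week 6 to Week 8, after children on azilsartan medoxomil (AZM) are re-randomised 1:1 to continue or switch to placebo.

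- **SAP 15.1.3** has treatment, Tanner stage, race and weight group "as fixed effects, and Week 6/Final Visit of the DB Phase seDBP as a covariate". Protocol 13.1.3 has the same blood pressure term ("as fixed effects, and Week 6/Final Visit of the DB Phase seDBP as covariate") but no race factor.
- **SAP Appendix 5, Step 4** programs this as "model score_c= trt wgtgrp tansgrp racegrp score_3/solution covb", where score_3 is Week 6. Day 1 (score_0) is not in the statement.
- **SAP Appendix 5, Steps 1 and 2** define "SCORE_0 - seDBP at time-point 0 (BASELINE, D1" and include it in the imputation: "var trt wgtgrp tansgrp racegrp score_0 score_1 score_2 score_3 score_5". Here score_5 is Week 8.
- **Protocol 6.1.4.1** places the Day 1 reading before the first double-blind dose: "pretreatment vital signs and a full panel of clinical laboratory tests will be completed" at Visit 4. It therefore precedes re-randomisation at Week 6.
- **SAP 7.1** lists baseline seDBP among the covariates in use but sends the reader to each analysis section for where it enters. Section 15.1.3 does not use it.

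**The concern.** Week 6 seDBP is one visit's on-treatment reading and carries measurement error. Day 1 seDBP is a second reading of the same child's underlying pressure. It is also the untreated level towards which a child switched to placebo would be expected to move. If it predicts Week 8 beyond what Week 6 already does, leaving it out makes the residual variance larger than it need be.

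A covariate fixed before re-randomisation leaves the treatment comparison unchanged and costs one degree of freedom. Precision is shortest in Steps 2 to 4 of the fixed sequence, where each dose has about 23 children and a failure at one step ends testing of the later ones.

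**Working it through.** **Inputs.** Protocol 13.3: 52 per arm, so 3 × 52 = 156 on AZM; 10% dropout; SD of change 8.3; difference 4.5 mm Hg; two-sided 0.05. Withdrawal allocation is 1:1 (Protocol 6.1).

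**Numbers analysed.** 156 × 0.9 = 140.4, or 70.2 continuing and 70.2 on placebo. One dose has 70.2 / 3 = 23.4 continuing, against the same 70.2 on placebo. The pooled contrast averages three dose means, so its variance is s²[(1/9)(3/23.4) + 1/70.2] = s²(2/70.2), as for a comparison of 70.2 with 70.2.

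**The plan's own figures.** Power comes from the noncentral t with noncentrality 4.5 / [s√(1/n₁ + 1/n₂)].
- Original: 195 × 0.9 / 2 = 87.75 per side, SD 10.5, power 80.6% (stated 80%).
- Revised: 70.2 per side, SD 8.3, noncentrality 3.21, power 89.1% (stated as above 80%).
- One dose at the same SD and difference: 61.3%. The plan states no power for this.

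These are unadjusted t-test figures, with no credit for any covariate.

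**Effect of adding Day 1.** The documents give no between-visit correlation. Assume each reading is a true level (between-child variance v) plus independent error of variance e, equal at all visits. The change then has variance 2e, so e = 8.3² / 2 = 34.4. The residual variance is
- with Week 6 only: v + e − v²/(v + e);
- with Week 6 and Day 1: v + e − v²/(v + e/2).

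| True between-child SD | Residual variance, Week 6 only | With Day 1 | Cut | Residual SD | Pooled power | One-dose power* |
|---|---|---|---|---|---|---|
| 4 | 45.37 | 42.74 | 5.8% | 6.74 → 6.54 | 97.6% → 98.2% | 79.1% → 81.4% |
| 6 | 52.05 | 46.09 | 11.4% | 7.21 → 6.79 | 95.6% → 97.4% | 73.4% → 78.5% |
| 8 | 56.84 | 48.02 | 15.5% | 7.54 → 6.93 | 94.0% → 96.9% | 69.6% → 76.8% |

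*If a single dose also had a 4.5 mm Hg effect.

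The cut equals the squared partial correlation of Day 1 with Week 8 given Week 6 (here about 0.24, 0.34 and 0.39). If that correlation is zero, so is the gain.

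**Entry selection.** Protocol 7.1 requires, for currently treated children, "a post-washout clinic seDBP meeting the above criteria on Day -1 (or Day 1 for subjects not participating in ABPM"); untreated children must meet the same threshold on that day as well. This narrows the spread of Day 1. I simulated the same model with the lowest part of the qualifying readings removed. The fraction removed is my assumption.
- Selection on Day 1 itself, lowest 50% removed: cuts of about 2%, 5% and 8%.
- Selection on Day 1 itself, lowest 30% removed: about 3%, 7% and 10%.
- Selection on a separate nearby reading, as for children in ambulatory monitoring who qualify on Day -1: the loss is smaller. With 50% removed the cuts were about 5%, 9% and 12%.

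Roughly 2% to 10% is a fair range, and a separate qualifying reading can reach slightly above it. The threshold is a percentile for age, gender and height, so in mm Hg it varies between children, which softens the truncation. Against that, Tanner stage and weight group are already in the model and would absorb part of what Day 1 carries.

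**The case against.** The plan is coherent as it stands. Adjusting a Week 6 to Week 8 change for its Week 6 starting value is a standard pre-specified model, the protocol and SAP agree on that covariate, and the stated power is met without it. All of this stands, and it limits the point to a missed improvement.

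Four stronger readings are tempting, and the documents do not support them.
- *The model adjusts only for Week 6.* It also has Tanner stage, race and weight group. Week 6 is only the sole blood pressure covariate.
- *Power starts from 89% pooled and 61% per dose, so the trial needs the covariate.* Those figures treat 8.3, the SD of the change, as the residual SD after adjustment. Under the assumptions above, Week 6 adjustment already brings power to about 94% to 98% and 70% to 79%.
- *The dose steps are under-powered against the plan's target.* The plan assumes 4.5 mm Hg for pooled AZM only. It states neither an effect nor a power for single doses.
- *Using Day 1 for imputation but not for analysis is an inconsistency.* An imputation model richer than the analysis model is ordinary practice. It shows only that the value is at hand and was thought informative.

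A fair further objection is that Week 4 seDBP would also serve as a second reading: it is taken at the final dose, is not used for entry and also precedes re-randomisation. That is true. The particular case for Day 1 is that it is the untreated level.

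**Conclusion.** The point holds as a modest, low-cost improvement. Day 1 seDBP is a valid covariate, is available, and is absent from the primary model. No bias or invalid test follows from its absence.

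The likely gain is a residual variance lower by roughly 2% to 10% once entry selection is allowed for, with 5.8% to 15.5% as the case without selection. In power, without selection, this is about 1 to 3 points on a pooled test that is already strong, and about 2 to 7 points on a dose step if that dose has a 4.5 mm Hg effect. Selection would make these gains smaller.

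The range rests on equal independent visit error, a between-child SD of 4 to 8 mm Hg and an assumed severity of selection. None of these is in the documents.

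**What to change.** Before treatment codes are released for the analysis in SAP 4.2, add Day 1 seDBP (score_0) as a second continuous covariate beside Week 6 seDBP in SAP 15.1.3, SAP 15.1.4 and the Step 4 model statement of Appendix 5. Record the change in SAP 3.6, which at present only points to the sample size section. The SAP has already added race to the protocol's model, so refining the covariates at this stage is not new here.

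The secondary analyses of seSBP and MAP in SAP 15.2.3.1 need a prior step. That section adjusts for a baseline value of seDBP or MAP, although the endpoints are seSBP and MAP. It is also unclear which visit is meant: SAP 6.2 and 7.1 point to Day 1, while Appendix 1 treats Week 6 as the Withdrawal Phase baseline. Settle this first, then include both the Week 6 and the Day 1 value of the parameter being analysed.

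The cost is SAP wording, one model term and one degree of freedom per analysis. No new data or visits are needed.
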